Clinical Study Protocol

Drug Substance	Roxadustat
Study Code	D5741C00002
Version	4.0
Date	06 July 2021

ALTAI: An Open-Label, Randomized, Active-Controlled, Parallel Design, Multicenter Phase IV Study to Investigate the Effect of Roxadustat versus Recombinant Human Erythropoietin (rHuEPO) on Oral Iron Absorption in Chinese Patients with Anemia of Chronic Kidney Disease (CKD)

Sponsor: AstraZeneca AB, [name]

VERSION HISTORY

Version 4.0, 06 July 2021

Changes to the protocol are summarized below.

For Inclusion criterion #4, it was clarified that the definition of adequate dialysis includes all values equal to or above those mentioned in the protocol by adding “ \geq ” to these values, ie, patients who have $\text{stdKt/V} \geq 2.1$ in HD, and total (renal + PD) weekly $\text{Kt/V} \geq 1.7$ in PD, are considered eligible as previously clarified in a protocol clarification letter.

For Inclusion criterion #17, it was clarified that COVID-19 tests are allowed to be performed after the first Screening Visit, but before the patient returns for the next study visit, if site procedures cannot be performed on the day of the first Screening Visit.

Exclusion criteria #33 and #34 were removed because they were no longer applicable under the amended statistical analysis plan.

The definition of dry weight was added in Table 1, footnote j.

It was clarified throughout the protocol that COVID-19 tests can be performed after the first Screening Visit, but before the patient returns for the next study visit, if site procedures cannot be performed on the day of the first Screening Visit.

The window of tolerance of ± 3 minutes for blood sampling timepoints for the ferrokinetic study was clarified throughout the protocol. It was also clarified that the ferrokinetic study on Day 1 must be completed prior to randomization and prior to the hemodialysis procedure on Days 1 and 15, and that patients randomized to the roxadustat group should take the roxadustat at least 6 hours before the ferrokinetic study starts on Day 15.

The benefit/risk assessment section was updated based on recent updates in the roxadustat package insert and Investigator Brochure.

The number of patients planned to be screened was updated from approximately to a maximum of 104 patients and the number of patients to be randomized was updated from a minimum of 46 to a minimum of 20 patients, which does not impact the assessment of the primary endpoint of the study. The target proportions of DD-HD, DD-PD, NDD-rHuEPO-users and NDD-rHuEPO-naïve patients were modified.

Details were added to clarify statistical analysis regarding population and efficacy analysis throughout the protocol.

It was clarified that information on pregnancy has to be provided to FibroGen Drug Safety, instead of AstraZeneca Patient Safety data entry site, within 1 calendar day for all pregnancies.

It was clarified that information on overdose has to be provided to FibroGen Drug Safety instead of AstraZeneca Patient Safety data entry site, and that all relevant information on medication errors has to be completed within 1 calendar day.

Minor editorial changes were made throughout the document, where required.

Version 3.0, 24 Jun 2020

Changes to the protocol are summarized below.

The Run-in Period was removed, and patients will now move directly from the Screening Period to the Treatment Period. After the addition of recombinant human erythropoietin (rHuEPO)-naïve non-dialysis dependent chronic kidney disease (NDD-CKD) patients to the study, the purpose of the Run-in Period was reconsidered. The Run-in Period was removed because the study team concluded that it would neither add scientific nor safety benefit to the study. The day of the end of the Treatment Period was corrected to Day 15. Concerns about any variability in haemoglobin (Hb) values in the patients randomized to rHuEPO for both rHuEPO-user and rHuEPO-naïve patients will be addressed with a Day 8 visit and local Hb test. All the Run-in Period activities will be performed during the Screening Period. Sections 1 (Protocol summary), 4 (Study Design), 5 (Study population), 6.1 (Treatments administered), and 7 (Discontinuation of treatment and patient withdrawal) were updated to clarify this.

To account for a potentially higher screen failure rate due to the patient recruitment measures during the coronavirus disease of 2019 (COVID-19) pandemic, it is anticipated that approximately 104 patients will need to be enrolled in the study. This is to ensure that a minimum of 46 patients (maximum 60) are randomized, with approximately equivalent number of patients in each stratum. The study will have competitive enrollment across all sites and strata. Sections 1.2 (Synopsis) and 4.1 (Overall design) were updated accordingly.

Inclusion criteria were widened to include patients who are non-dialysis-dependent and rHuEPO-naïve. Patients stratification at randomization will be done by dialysis status (dialysis-dependent [DD] versus non-dialysis-dependent [NDD]). Within the NDD strata, patients will be further stratified at randomization by rHuEPO-exposure (rHuEPO-naïve vs rHuEPO-users). Within the DD strata, patients will be stratified at randomization by type of dialysis (hemodialysis [HD] vs peritoneal dialysis [PD]). When rHuEPO-exposure in

NDD, and dialysis type in DD were introduced as stratification factors, high-sensitivity C-reactive protein (hs-CRP) was dropped as a stratification factor since it resulted in more strata than could be accommodated by the planned sample size, with a risk that some strata would remain empty or difficult to fill. The change in stratification further reduces complexity in the analyses. Each stratum is planned to have an equivalent number of patients. Sections 1.2 (Synopsis), 2.1 (Study rationale), 4.1 (Overall design), 6.3 (Measures to minimize bias: randomization and blinding) and 9 (Statistical considerations) were updated to clarify this.

Instruction regarding contraceptive methods to be used by study participants was updated per the roxadustat package insert in Section 5.1 (Inclusion criteria), and exposure to iron-chelating agents within the 6 weeks prior to the Screening Visit was updated in Section 5.2 (Exclusion criteria).

Section 2.3 (Benefit/risk assessment) was updated with roxadustat safety information, and a benefit/risk assessment and risk mitigation plan in view of the coronavirus disease of 2019 (COVID-19) pandemic.

The purpose and schedule of dose adjustments for rHuEPO and roxadustat, and plan for post-study treatments for both, the rHuEPO and roxadustat arms, were clarified in Sections 1.2 (Synopsis), 4.1 (Overall design), and 6.1 (Treatments administered). The permissible methods of administration of rHuEPO were clarified in Sections 6.1.2 (Dose of study treatments) and 6.2 (Preparation/handling/storage/accountability).

Section 8.2.4 (Electrocardiograms) was updated to replace triplicate electrocardiogram (ECG) measurements with single measurements.

The study design, patient population, risk mitigation strategy, statistical considerations, and provisions for patient withdrawal were updated in view of the COVID-19 pandemic in Sections 1.1 (Schedule of activities), 2.3 (Benefit/risk assessment), 4 (Study design), 5.1 (Inclusion criteria), 5.4 (Screen failures), 7.3 (Withdrawal from the study), 8.3 (Collection of adverse events), and 9.4 (Statistical analyses).

Minor editorial changes were made throughout the document, where required.

Version 2.0, 05 July 2019

Changes to the protocol are summarized below.

The dosing for recombinant human erythropoietin (rHuEPO) was changed from 3 times a week (TIW) to allow TIW or 2 times a week (BIW) for the lowest dose of rHuEPO. For

patients on a weekly dose of rHuEPO of 6000 IU, dosing will be BIW (ie, 3000 IU BIW) and for patients on a weekly dose of rHuEPO of >6000 IU, dosing will be TIW. This is due to unavailability of 2000 IU prefilled syringes of rHuEPO. Section 1 (Protocol summary), Section 4 (Study design) and Section 6 (Study treatments) were updated to reflect this change.

Timepoints for dispensation of rHuEPO was clarified in Section 1 (Protocol summary).

The number of patients to be randomized was updated in Section 1 (Protocol summary), Section 4 (Study design) and Section 6 (Study treatments) to reflect a minimum of 46 patients will be randomized, to allow some flexibility in the final number of randomized patients, as it will be difficult to control recruitment to stop at exactly 46 randomized patients.

The primary and secondary assessments text in Section 1 (Protocol summary), Section 8.1 (Efficacy assessments) and Section 9.4 (Statistical analyses) was updated to improve clarity on stratification factors.

Footnote 'a' in the schedule of activities Table (Table 1- Section 1 [Protocol summary]) was updated to clarify that results from the Screening Period for transferrin saturation (TSAT), ferritin, vitamin B12, serum folate, alanine aminotransferase (ALT), aspartate aminotransferase (AST), high-sensitivity C-reactive protein (hs-CRP) and total bilirubin (TBL) must be available prior to starting the Run-in Period .

It was clarified in Section 1 (Protocol summary), Section 4 (Study design) and Section 6 (Study treatments) that study treatment dosing must occur on the days of the ferrokinetic study (ie, on the days of Visit 4 and 6).

It was clarified in Section 5 (Study population) that inclusion criteria #8 and #9 would be obtained from the Screening Visit (Visit 1).

It was clarified in Section 5 (Study population) that inclusion criteria #12 and #13 referred to Visit 1 (Screening Period) and inclusion criteria #14 referred to both Visit 1 (Screening Period) and Visit 2 (start of Run-in Period).

It was clarified in Section 5 (Study population) for inclusion criteria #14, that ALT or AST and TBL would be obtained from Visit 1, Screening Visit or Visit 2, start of Run-in Period.

It was corrected in Section 5 (Study population) for inclusion criteria #14, that ALT or (not and) AST must be <3 x upper limit of normal (ULN). There was a typographical error in the original protocol – and has been corrected to or.

Section 6.5 was updated to clarify that patients taking iron before the study could not change the dose during the Treatment Period.

New text on malignancy was added to Appendix B (Adverse events definitions and additional safety information) to reflect changes being made to the TransCelerate clinical study protocol template.

Version 1.0, 17 May 2019
Initial creation

This Clinical Study Protocol has been subject to a peer review according to AstraZeneca standard procedures. The Clinical Study Protocol is publicly registered and the results are disclosed and/or published according to the AstraZeneca Global Policy on Bioethics and in compliance with prevailing laws and regulations.

TABLE OF CONTENTS

TITLE PAGE.....	1
VERSION HISTORY	2
TABLE OF CONTENTS	7
1 PROTOCOL SUMMARY	11
1.1 Schedule of activities (SoA).....	11
1.2 Synopsis	17
1.3 Schema	24
2 INTRODUCTION.....	25
2.1 Study rationale.....	25
2.2 Background	26
2.3 Benefit/risk assessment.....	26
2.3.1 Risk assessment and mitigation pertinent to COVID-19 pandemic	28

1 PROTOCOL SUMMARY

1.1 Schedule of activities (SoA)

The schedule of activities (SoA) for the study is shown in [Table 1](#) below. The study consists of 3 periods: the Screening Period, Treatment Period and Follow-up Period.

Table 1 Schedule of activities

	Screening Period ^{a,b}	Treatment Period ^b			Discontinuation ^{b,c}	28-day Follow-up Period ^{c,d}	Details in CSP or Appendix section
Day	< -21 > -14 to 0	1	8 -1/+2 days	15 ± 2 days		43 ± 3 days	
Visit	1, 1a and 1b ^e	2	3	4		5	
Pre-screening telephone contact ^f							Section 4.1.1
Sign written ICF	X						Section 5 and Appendix A 3
Swab test for active COVID-19 infection ^g	X						Section 4.1.1
Eligibility criteria	X	X					Section 5
Demographics, medical and surgical history, and prior medication	X						Section 5
Hematology/hemostasis ^h	X ⁱ	X	X	X	X		Sections 5 and 8.2.1
HbA1C	X						Section 8.2.1
iPTH	X						Section 8.2.1
Physical examination, dry body weight ^j	X						Sections 5 and 8.2.2
Clinical chemistry ^k	X	X		X	X		Section 8.2.1
Urinalysis ^l	X	X		X	X		Section 8.2.1
Vital signs ^m	X	X	X	X	X		Sections 5 and 8.2.3
12-lead ECG	X						Section 8.2.4
Liver function tests ⁿ	X	X		X	X		Sections 5 and 8.2.1
Iron profile ^o	X	X		X	X		Sections 5 and 8.1
Hepcidin		X		X	X		Section 8.1
hs-CRP	X	X		X	X		Section 8.1

	Screening Period ^{a,b}	Treatment Period ^b			Discontinuation ^{b,c}	28-day Follow-up Period ^{c,d}	Details in CSP or Appendix section
Day	< -21 > -14 to 0	1	8 -1/+2 days	15 ± 2 days		43 ± 3 days	
Visit	1, 1a and 1b ^e	2	3	4		5	
Vitamin B12, folate	X						Sections 5 and 8.2.1
Terminate IV iron + TRIFERIC [®] in dialysate ^p	X						Section 5
Single dose of oral iron (12.5 mL [100 mg elemental iron]) administration		X ^q		X ^q	X		Section 6.1.3
Ferrokinetic study (T0 ^f , 1, 2, 3 hours)		X ^{q,r}		X ^{q,r}	X		Section 8.1
Concomitant medications	At every visit after Visit 1 and may be conducted by phone if not tied to a visit						Section 6.5
Routine safety measurements							
Adverse events	At every visit after Visit 1 and may be conducted by phone if not tied to a visit						Section 8.3
Serum pregnancy test ^s	X	X					Section 8.2.1
Study treatment administration							
Randomization ^t		X					Section 6.3 and Section 4.1.2
Study treatment dispensed ^u		X	X ^v				Section 6
Study treatment (rHuEPO and roxadustat) compliance			X	X	X		Section 6

^a The Screening Period will be approximately 2-3 weeks long, but may be greater or lesser, to ascertain the Hb eligibility criteria with up to 3 Hb tests. To check Hb eligibility criteria, Hb levels must be assessed twice, at least 7 days apart, during the Screening Period; Hb levels may be assessed up to 3 times (Visits 1, 1a and 1b) during the Screening Period. The rHuEPO dose may be adjusted during the Screening Period for patients who were on rHuEPO before the Screening Period depending on the patient's Hb levels, at the discretion of the Investigator, in accordance with the rHuEPO China Package Insert. Results for Screening Period assessments for TSAT, ferritin, vitamin B12, serum folate, ALT, AST, hs-CRP and TBL must be available prior to starting the Treatment Period.

- b Each patient will be contacted within 24 h before a scheduled visit to confirm that he/she has no symptoms of COVID-19 infection and that he/she has had no contact with a known COVID-19 positive person within the past 14 days. If the patient reports symptoms or contact with a COVID-19-positive patient within the past 14 days, the Investigator may ask the patient to be tested for active COVID-19 infection (swab test to rule out active COVID-19 infection), or withdraw the patient from the study, as is most suitable for the patient's safety, at the Investigator's discretion. The study treatment and assessments may be continued as planned until the swab test results are available, at the discretion of the Investigator. Patients who test positive on the swab test must be withdrawn from the study. A patient who contacts the site at any time during the Treatment Period informing that he/she has symptoms suggestive of COVID-19 may be asked to get tested for active COVID-19 infection, or be withdrawn from the study for safety reasons, at the Investigator's discretion. Patients who test positive (for COVID-19) must be withdrawn from the study. Any study assessments planned on the days of site visits may be completed via a telephone call and/or a visit to the patient's home, as required, and if possible. The handling of patients and their blood or urine samples will be done using sterile techniques and observing precautions for infection control and prevention. Reasons for delayed site visits will be reported as protocol deviations. The actual dates when the visit-related assessments were completed will be recorded in the eCRFs.
- c Applicable for discontinuation prior to the end of the Treatment Period. Patients who discontinue study treatment early should be asked to return to the study site for the discontinuation visit within 7 days after the study treatment is stopped, and for the Follow-up Visit 28 days later unless consent to participate is withdrawn. Patients who withdraw prior to the end of the Treatment Period due to a positive COVID-19 test result should not attend the Discontinuation Visit or the 28-day Follow-up Visit at the study site. The assessments planned for the Discontinuation and 28-day Follow-up Visit should be completed via a telephone call, as far as possible. See Section 7.1.3 for details.
- d May be conducted over the phone.
- e All patients should attend Visits 1 and 1a at the clinical site. All patients will be tested for COVID-19 infection at the first Screening Visit (Visit 1)^e. Patients may attend Visit 1b at the clinical site, if needed, to assess Hb level (see footnote i).
- f Each patient will be contacted before the first Screening Visit (Visit 1) to confirm that he/she has no symptoms of COVID-19 and that he/she has had no contact with a known COVID-19 positive person within the past 14 days. Only asymptomatic patients, or those who have had no contact with a known COVID-19 positive person within the last 14 days, will be asked to come to the site for informed consent and eligibility screening procedures.
- g All patients will be tested for COVID-19 infection at the first Screening Visit, using a swab test to rule out active infection for COVID-19. If according to site procedures the test for COVID-19 infection cannot be performed at the first Screening Visit, the test should be performed as soon as possible thereafter but must be performed before the patient returns for the next study visit. Patients who test positive must be withdrawn from the study. All samples (blood and urine) for eligibility assessment will be collected at Visit 1 during the Screening Period, while the swab test results are awaited. The handling of patients and their blood or urine samples will be done using sterile techniques and observing precautions for infection control and prevention.
- h Red blood cell, Hb, hematocrit, leukocyte count, leukocyte differential count, platelet count, MCV, reticulocytes. On Days 1 and 15, blood samples for these assessments will be collected **before** time T0 (ie, **before administration of the single dose of oral iron**). On Days 1, 8, and 15 hemoglobin levels will be tested in the central laboratory for all patients. Additionally, for patients randomized to rHuEPO, Hb levels will be tested in the local laboratory on Days 1 and 8 for initial dose determination and dose adjustment. The rHuEPO dose may be adjusted on Day 8 of the Treatment Period, depending on the patient's Hb levels, for safety reasons as determined by the Investigator, in accordance with the rHuEPO China Package Insert. On Day 15 (or at the discontinuation visit), Hb levels will be tested in the local laboratory for all patients who were on rHuEPO prior to the study, to decide what rHuEPO dose to re-start patients on, or another appropriate course of treatment for anemia, after study treatment stops. For patients who were rHuEPO-naïve before entering the study, Hb levels may be tested in the local laboratory on Day 15 (or at the Discontinuation Visit) at the discretion of the Investigator, to determine an appropriate course of treatment for anemia in each patient.
- i To check Hb eligibility criteria, Hb levels must be assessed in the central laboratory twice, at least 7 days apart, during the Screening Period; Hb levels may be assessed up to 3 times (Visits 1, 1a and 1b) during the Screening Period.

- j Body weight for HD patients should be the patient's dry weight. Dry weight - also known as optimum postdialysis weight - is the postdialysis weight at which all or most excess body fluid has been removed. Weight for patients on PD should be obtained with a "dry" or empty peritoneal cavity (PD fluid fully drained).
- k Glucose, calcium, sodium, potassium, bicarbonate, chloride, BUN, creatinine, magnesium, phosphorus.
- l Urine dipstick glucose, protein and blood performed locally (applicable for non-dialysis-dependent patients, and dialysis-dependent patients who are not anuric).
- m Vital signs will include tympanic temperature, systolic and diastolic BP, pulse rate and respiratory rate. Blood pressure should be measured prior to the hemodialysis procedure. For patients on PD, BP should be measured in the morning prior to the patient performing the first exchange of the day. Pulse rate and BP should be measured in triplicate after being comfortably at rest in a seated position with the back and feet supported (ie, by chair back and floor or platform, respectively) quietly for at least 5 minutes.
- n Alanine aminotransferase, AST, ALP, albumin, and TBL.
- o Serum iron, ferritin, TIBC, TSAT, transferrin, soluble transferrin receptor. On Days 1 and 15, blood samples for these assessments will be collected **before** time T0 (ie, **before administration of the single dose of oral iron**). Note that serum iron and TIBC are included in the ferrokinetic study and should not be taken as part of the iron profile as well on Days 1 and 15. There is no need to collect duplicate sample for serum iron and TIBC. The sample collected before the single dose of oral iron is administered can serve for the iron profile as well.
- p Intravenous iron and TRIFERIC® in dialysate should be stopped at the Screening Visit (ie, at Visit 1) and should not be taken after stopping, throughout the Screening and Treatment Periods, but can be started again after the Treatment Period.
- q Must be conducted prior to randomization at Day 1 and prior to the hemodialysis procedures at Days 1 and 15.
- r The blood samples for the ferrokinetic study (serum iron and TIBC) must be taken immediately **before** the single dose of oral iron is administered (ie, immediately before time T0), and then at T1, T2 and T3 after the single dose of oral iron (sample for serum iron only). The window of allowance for the ferrokinetic study blood sampling will be ±3 minutes.
- s Collect from female patients of childbearing potential only.
- t Results for Screening Period assessments for **ALT, AST and TBL must be available before randomization**. Randomization must occur after the ferrokinetic study has completed, ie, after collection of the T3 serum iron sample. Patients will be randomly assigned in 1:1 ratio to either roxadustat or rHuEPO. Study treatment to be administered after randomization at Day 1.
- u Patients will receive either roxadustat (orally) or rHuEPO (IV or SC) during the Treatment Period. Roxadustat will be administered TIW. For patients on a weekly dose of rHuEPO of 6000 IU, dosing will be BIW (ie, 3000 IU BIW) and for patients on a weekly dose of rHuEPO of >6000 IU, dosing will be TIW. The dose of study treatment administered will be recorded.
- v For patients randomized to the rHuEPO arm, Hb levels will be tested in the local laboratory on Day 8, and the rHuEPO dose may be adjusted depending on the patient's Hb levels, for safety reasons, as determined by the Investigator. Study treatment dispensation will only occur for patients on the rHuEPO arm, not patients on the roxadustat arm (as only the rHuEPO dose may be adjusted at this visit). The roxadustat dose will not be adjusted during the Treatment Period; therefore, for patients on the roxadustat arm Hb samples will not be collected on Day 8 for testing in the local laboratory.

ALP=alkaline phosphatase; ALT=alanine aminotransferase; AST=aspartate aminotransferase; BIW=2 times a week; BP=blood pressure; BUN=blood urea nitrogen; eCRF=electronic case report form; COVID-19=coronavirus disease of 2019; CSP=clinical study protocol; ECG=electrocardiogram; Hb=hemoglobin; HbA1C=hemoglobin A1C; HD=hemodialysis; hs-CRP=high-sensitivity C-reactive protein; ICF=informed consent form; iPTH=intact parathyroid hormone; IU=International Unit; IV=intravenous; MCV=mean corpuscular volume; PD=peritoneal dialysis; rHuEPO=recombinant human erythropoietin; SC=subcutaneous; TBL=total bilirubin; TIBC=total iron binding capacity; TIW=3 times a week; T0=time at which single dose of oral iron will be administered at the start of ferrokinetic study; TSAT=transferrin saturation.

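### The pre-screening COVID-19 call checks for no symptoms and no contact, but the sentence deciding who comes to the site joins the two conditions with 'or'

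*Protocol*

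**What the plan says.** Protocol Section 1.1, Table 1 footnote f, sets out the pre-screening telephone contact in two sentences.

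- **Purpose of the call:** "to confirm that he/she has no symptoms of COVID-19 and that he/she has had no contact with a known COVID-19 positive person". The look-back period for contact is 14 days.
- **Who attends:** "Only asymptomatic patients, or those who have had no contact with a known COVID-19 positive person within the last 14 days, will be asked". The invitation is to attend the site for informed consent and eligibility screening.

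The same pair of sentences, with only trivial differences, appears in Section 1.2 (Synopsis, treatments and treatment duration) and at the start of Section 4.1.1.

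Three other provisions bear on it:

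- **Footnote b**, on the call within 24 hours before a scheduled visit: "If the patient reports symptoms or contact with a COVID-19-positive patient within the past 14 days, the Investigator may ask the patient to be tested", or may withdraw the patient. Treatment and assessments may go on until the swab result is known, at the Investigator's discretion.
- **Footnote g:** "All patients will be tested for COVID-19 infection at the first Screening Visit, using a swab test to rule out active infection for COVID-19". Where site procedures prevent this, the swab may be taken afterwards, provided it is done before the next visit. Eligibility samples are collected at Visit 1 while the result is awaited, under infection-control precautions. A positive test means withdrawal.
- **Section 2.3.1** describes CKD patients as having weakened immune systems. It names suggestive symptoms or a recent contact as situations that the protocol's measures are meant to address.

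**The concern.** The first sentence joins the two conditions with *and*; the second joins them with *or*. The second is the operative one, because it determines who is asked to travel to the site. A coordinator who follows it to the letter may invite a symptomatic patient with no known contact, or a symptom-free patient who is a known contact. Neither meets both conditions that the call is meant to confirm.

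What is at stake is infection control at sites that treat a vulnerable population, and uniform handling of the call across the approximately 7 to 10 sites. Checking another section does not help a site, because all three statements carry the same mismatch. No eligibility criterion in Sections 5.1 or 5.2 names recent contact. Inclusion criterion 17 concerns the swab result and recovery from past infection, and exclusion criterion 13 rests on the opinion of the Investigator or Sponsor.

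**Working it through.** The plan gives no figure to reproduce. The check is a comparison of the two sentences over every possible answer to the call, followed by a comparison with the related provisions.

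**Step 1. Inputs.** Let S be *no symptoms* and C be *no known contact within 14 days*. The purpose sentence corresponds to S and C. The invitation sentence corresponds to S or C.

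**Step 2. Truth table.**

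| Symptoms | Contact | Purpose: S and C | Invitation: S or C |
|---|---|---|---|
| No | No | met | invited |
| No | Yes | not met | invited |
| Yes | No | not met | invited |
| Yes | Yes | not met | not invited |

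The purpose sentence is met in 1 of 4 combinations and the invitation sentence in 3 of 4. They disagree in 3 − 1 = 2 combinations, which are those with exactly one risk factor. Only a patient with both is turned away by the literal rule.

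These are counts of combinations, not proportions of patients. The protocol gives neither the number of patients to be telephoned nor the frequency of symptoms or contact, so the number affected cannot be derived from it.

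**Step 3. Comparison with footnote b.** There, *or* joins the two risk factors (symptoms, or contact), so either one alone prompts consideration of a test or withdrawal. In footnote f, *or* joins the two absences of risk, so either absence alone is enough to be invited. A patient with one risk factor therefore passes footnote f and would trigger footnote b. Sections 4.1.1, 7.3 and 8.2.1 repeat the logic of footnote b, and Section 2.3.1 also names the two factors as alternatives.

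**Step 4. Timing of the swab.** Written consent must come before any screening test, and the invitation under footnote f is to attend for that consent. The swab therefore cannot come before arrival, and footnote g lets it follow Visit 1. It does not replace the telephone rule in deciding who enters the site.

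**The case against.** The strongest reply is that this is a drafting slip which its context resolves. The preceding sentence states both conditions, footnote b shows that either factor alone matters, and many sites would apply both without being told. That is a fair reading of the probable intent. It does not cure the text, since the sentence that governs action says something else wherever it appears.

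The reply also limits how far the point can go, and it is right on each of these:

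- **A reader might infer that the call is the only barrier at Visit 1.** The documents do not support that. The Screening Period column of Table 1 carries the footnote b marker, so the call within 24 hours before a scheduled visit extends to screening, although Section 4.1.1 sets its version out under the Treatment Period. Footnote g adds precautions for handling patients and samples, the swab is taken at Visit 1 by default, and Section 2.3.1 calls for an individual risk assessment.
- **A reader might infer that footnote b bars such patients and that footnote f therefore breaches it.** Footnote b bars no one on symptoms or contact alone. It gives the Investigator discretion and allows assessments to continue while a result is awaited. The outright contradiction is between the two adjacent sentences; against footnote b the mismatch is one of logic.
- **A reader might infer that wrongly invited patients use up places under the 104-patient screening maximum.** Section 5 defines screened patients as those who fulfil the eligibility criteria. A swab-positive patient fails inclusion criterion 17 and is not screened in that sense. Section 5.4 also allows one rescreening for this criterion.

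**Conclusion.** The inconsistency is real and stands in all three statements of the rule. Read literally, the invitation sentence admits both one-risk-factor combinations, which the stated purpose of the call does not support. It is a minor site-safety inconsistency, worth correcting because it concerns the protection of patients and staff and costs almost nothing to remove.

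The conclusion rests only on the wording and on taking the second sentence as the operative one. It needs no assumption about infection rates. A reader might want to turn the 3-of-4 count into an expected number of patients, but the documents offer no basis for that.

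The primary endpoint, significance level, power, sample size, randomization and analysis are all untouched. A patient who tests positive must be withdrawn whichever sentence the site followed.

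**What to change.** Reconcile the two sentences in Table 1 footnote f, Section 1.2 and Section 4.1.1 so that the rule for inviting patients agrees with the stated purpose of the call and with the either-factor logic of footnote b. All three places need the change, since correcting footnote f alone would leave the Synopsis and Section 4.1.1 in conflict with it.

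The cost is one sentence in three places. The version history shows that a protocol clarification letter was already used for the wording of inclusion criterion 4, so the sponsor has a precedent for handling such a point. The small downside is that a few patients may be called to the site later than they otherwise would be. No statistical section needs to change.
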